13.1.3. Adverse Event Reporting Period

The investigator must start reporting non-serious AEs starting with the subject’s first study medication treatment continuing until the subject’s last study visit. Non-serious adverse events that occur between the time the subject was consented and the first application of study medication will be reported as medical history.

Reporting for SAEs begins after the subject signs the informed consent and continues until the subject’s last study visit (regardless of relationship to study medication). If a subject experiences a SAE after the subject’s last study visit, that is deemed by the investigator to be related to study medication, the investigator must report this to the Sponsor using the study specific SAE report form.

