4.2. Study Rationale

The rationale for the dose selection and treatment design of A-101-WART 301 and A-101-WART-302 and this open label, long term safety study is based on data collected from three completed (3) Phase 2 studies which assessed dose response and dose frequency of A-101 (H_2O_2) Topical Solution in patients with common warts. All three studies demonstrated good efficacy and safety of H_2O_2 45% for the treatment of common warts.

The three studies conducted are identified below and they represent data collected from 406 subjects.

- **Study A-101-WART-201:** A Randomized, Double-Blind, Vehicle-Controlled, Parallel- Group, Study of A-101 Solution in Subjects with Common Warts (n=90).
- **Study A-101-WART-202:** A Randomized, Double-Blind, Vehicle-Controlled, Parallel Group Study of A-101 Topical Solution Applied Once a Week in Subjects with Common Warts (n=157).
- **Study A-101-WART-203:** A Randomized, Double-Blind, Vehicle-Controlled, Parallel Group Study of A-101 Topical Solution Applied Twice a Week in Subjects with Common Warts (n=159)

Aclaris Therapeutics, Inc.

Protocol Number: A-101-WART-303

Protocol: Version 3: 14 February 2019

On the basis of these successful Phase II studies, Aclaris has progressed to phase III with studies A-101-WART 301 and A-101-WART-302. These studies will assess efficacy and safety of 8 weeks of treatment and 12 weeks of post treatment follow up. Aclaris recognizes that many patients may require multiple treatment courses and there is therefore a need to assess the long-term safety of topical H₂O₂ 45%. A-101-WART-303 is therefore designed to assess the long-term safety of patients who were initially treated in studies A-101-WART-301 and A-101-WART-302.

Aclaris Therapeutics, Inc.

Protocol Number: A-101-WART-303

Protocol: Version 3: 14 February 2019

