⁴ Investigational site staff will be required to make a phone contact with the subject on Day 15, Day 43, Day 102 and Day 144 to assess for any safety issues and possible new concomitant medications the subject may have started taking. In addition, subjects are to ask if they have had any new warts develop since the last in office visit.

⁵ Subjects over the age of 18 are to apply the A-101 study medication on the following days: Day 1, Day 4, Day 8, Day 11, Day 15, Day 18, Day 22, Day 25, Day 29, Day 32, Day 36, Day 39, Day 43, Day 46, Day 50 and Day 53. A window of +1 day is allowed. Subject between the ages of 1-17 will have their A-101 study medication applied by a parent or guardian. Parents/legal guardians of children must ensure that the child does not put the treated area in their mouth, or eyes, until completely dry after the application. If the treated area is not completely dry 10 minutes after the application, the area should be blotted dry.

⁶ A-101 will only be dispensed to subjects who have not cleared all their warts, or who have developed new warts, and will be starting a new 8-week treatment cycle.

Table 3 Safety Observation Assessments for Subjects that are Clear at Visit 1 and Remain Clear

Visit	V1	V2	V3	V4	EOS
Treatment Day	Day 1	Week 6 (Day 42)	Week 12 (Day 84)	Week 18 (Day 126)	Week 26 (Day 182)
Window		+7 Days	+ 7 Days	+ 7 Days	+ 2 Days
In Office Visit	▲ ¹				▲

Aclaris Therapeutics, Inc.

Protocol Number: A-101-WART-303

Protocol: Version 3: 14 February 2019

Visit	V1	V2	V3	V4	EOS
Phone Call		▲ ²	▲ ²	▲ ²	
Informed Consent	▲				
Inclusion Criteria/Exclusion Criteria	▲				
Concomitant therapies		▲	▲	▲	▲
Adverse Events	▲	▲	▲	▲	▲

¹Visit 1 of A-101-WART 303 may occur on the same day as Visit 13 of A-101-WART 301 or A-101-WART 302.

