² Investigational site staff will contact via a documented phone call on Visit 2 Day 42, Visit 3 Day 84, Visit 4 Day 126 and Visit 5 Day 182. During the phone calls sites are to ask the subject if they have had any new warts develop or if a wart that was previously treated has recurred. If a subject has had a new wart develop or a previously treated wart has recurred, then the subject is to be scheduled for an in -office visit to start an 8-week treatment course with A-101 study medication. Subjects are to be instructed to contact the investigational site as soon as they think a new wart (or a recurrence) has developed. The 8-week treatment period can start no later than Day 122. Refer to Table 2 for the 8- week treatment schedule.

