9.3. Phone Call Visits

Subjects that are enrolled to the study that do not have any identified warts to be treated will complete the Visit 1 (can be the same day as V13 of A-101-WART-301 or A-101-WART-302) assessment in the office and then will have telephone contact visits on Day 42, Day 84, and Day 126. During these calls site staff will ask the subject if they have any adverse events that they feel are related to their previous treatment with A-101 Topical Solution and if they have had a new wart develop or if they have had a recurrence of a wart that was previously treated on the A-101-WART 301 or A-101-WART 302 study. If a subject has a new wart or a recurrence they can be scheduled for an in-office visit and initiate treatment on another 8-week treatment period with A-101 study medication. If an 8-week treatment period is started then all assessments outlined in Table 2 must be followed. A subject cannot start an 8-week treatment period after study Day 122.

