10. STUDY TREATMENT

10.1. Investigational Study Medication

The study medication for this study is open label A-101 45%. All study medications are clear, colorless solutions which are indistinguishable in physical appearance.

Table 4: Study Medication Information

Study Medication Name	A-101 45%
Manufacturer	James Alexander Corporation, Blairstown NJ
A-101 concentration (%)	45
Pharmaceutical Form	Solution
Storage Conditions	59°F to 77°F (15°C to 25°C) protected from excessive heat, open flame and combustibles, out of direct sunlight and in a well-ventilated, dry area*
Route	Topical
Frequency	A-101 Study Medication will be applied twice a week for 8 weeks.
Duration of Administration	Apply study medication to each identified common wart for approximately 15 seconds. Allow each treated wart to remain undisturbed for approximately 15 seconds. Repeat the application/waiting cycle until the study medication has been applied to each identified common wart up to 3 times.
Activated Applicators	Activated applicators are stable for 4 hours at room temperature (59°F to 77°F or 15°C to 25°C)

*Excursions from these temperature ranges must be reported to Aclaris.

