12.2. Clinical Laboratory Sampling

Subjects that do not have their Visit 1 the same day as Visit 13 of either A-101-WART 301 or A-101-WART 302 will have to have a clinical chemistry and CBC performed. Non-fasting blood samples for clinical laboratory analysis will be collected by a qualified staff member on Day 182 for all subjects. Approximately 7.5 mL of blood will be collected for each chemistry sample and 3 ml of blood will be collected for each complete blood count (CBC). These blood samples will be sent to a central laboratory for analysis. Refer to the study specific laboratory manual for instructions regarding handling of the blood samples and shipping instructions.

The following tests, at a minimum, will be conducted:

Chemistry Panel	Complete Blood Count
Albumin	Hematocrit
Alkaline phosphatase	Hemoglobin
Alanine aminotransferase (ALT)	Platelet count
Aspartate aminotransferase (AST)	Red blood cell morphology
Blood urea nitrogen (BUN)	Red blood cell count
Bicarbonate	White blood cell count
Calcium	White blood cell differential
Chloride	% & absolute
Creatinine	Basophils
Glucose	Eosinophils

Aclaris Therapeutics, Inc.

Protocol Number: A-101-WART-303

Protocol Version 3: 14 February 2019

Lactate dehydrogenase (LDH)	Lymphocytes
Phosphorus	Monocytes
Potassium	Neutrophils
Sodium	
Total bilirubin	
Total protein	
Uric acid	

The results of the clinical laboratory tests will be reported on the central laboratory's standard reports. These laboratory results will be sent to the investigator via fax. The investigator must review all laboratory reports in a timely manner and note NCS or CS to define the clinical relevance of any result that is outside the normal range for the laboratory. The investigator must date and initial every laboratory report.

The investigator must report all laboratory results that are BOTH outside the normal range for the laboratory AND, in the opinion of the investigator, CS as medical history if found prior to the first study medication treatment or as an AE if found after the first study medication treatment begins.

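### Non-serious AE reporting opens only at the first open-label A-101 application, so subjects who enter clear and stay untreated have no AE reporting period, contrary to Table 3

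*Protocol*

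**What the plan says.** Protocol Section 13.1.3 starts the reporting of non-serious AEs at the subject's first treatment with study medication. Non-serious events arising "between the time the subject was consented and the first application of study medication will be reported as medical history". SAEs are reported from consent. Section 10.1 identifies the medication: "The study medication for this study is open label A-101 45" per cent.

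Two other places use the same trigger. Section 12.2 reports a clinically significant out-of-range laboratory result as medical history before the first treatment, and "as an AE if found after the first study medication treatment begins". The last line of 13.1.1 does the same for clinically significant abnormalities in general.

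Other parts of the protocol expect AE data from subjects who are not treated. Table 3 is titled "Safety Observation Assessments for Subjects that are Clear at Visit 1 and Remain Clear" and marks AEs at V1, V2, V3, V4 and EOS. Section 9.3 has site staff ask these subjects, on the Day 42, 84 and 126 calls, about "any adverse events that they feel are related to their previous treatment with A-101 Topical Solution". Section 13.2.1 elicits AEs at every visit after enrolment and requires CRF entry for AEs noted in the reporting period. Section 14.4 lists safety summary groups of untreated subjects, split by parent-study arm.

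SAP 3.1 and 3.11 restrict safety summaries to subjects who received at least one application. SAP 3.14 says that data on untreated subjects will be listed.

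**The concern.** A subject who enters clear and never develops a wart never has a first application, so the event that opens AE reporting never happens. Yet the protocol schedules five AE contacts for exactly that subject. The 9.3 calls sharpen the conflict: a non-serious event that the subject attributes to earlier A-101 would be solicited by one section and sent to medical history by another.

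The primary objective is long-term safety, and Section 4.2 says "A-101-WART-303 is therefore designed to assess the long-term safety of patients who were initially treated in studies" A-101-WART-301 and A-101-WART-302. Followed literally, 13.1.3 leaves the off-treatment observation of clear subjects with SAEs only. The AE severity, causality and follow-up rules (13.1.4, 13.1.5, 13.2.1) do not reach an event held as medical history. If the listing of untreated subjects then showed no non-serious AEs, a reader could not tell whether none occurred or none was eligible to be entered.

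**Working it through.** **The trigger.** Section 13.1.3 does not itself say open-label. The reading follows from 10.1 and from the interval that 13.1.3 describes, which runs from consent to first application. If the first application were the parent-study dose, it would precede consent to this study and the interval would be empty.

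**The passages side by side**, for a subject who enters clear and stays untreated:

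| Protocol place | Consequence for this subject |
|---|---|
| 13.1.3 | Non-serious AE reporting never starts |
| 12.2; last line of 13.1.1 | A clinically significant result is never an AE, although 12.2 plans Day 182 blood samples for all subjects |
| Table 3 | AEs assessed at all five visits |
| 9.3 | Asked about AEs at three calls |
| 13.2.1 | AEs elicited at each visit after enrolment, but CRF entry is tied to a reporting period that does not exist |
| 14.4 | Belongs to a planned safety summary group |

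No passage reconciles the first two rows with the last four.

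**Subjects treated later.** The Table 3 footnote says "The 8-week treatment period can start no later than Day 122". The longest closed period is therefore 122 − 1 = 121 days after Day 1. (The SAP's copy of that footnote gives Day 102, which would make it 101 days; SAP 2 and 3.3 give Day 122.)

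**How many subjects.** Inputs from Protocol 14.1: 400 enrolled, 200 of them from the active arms, and 26% of warts clear at the end of the parent studies.

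- The plan's own figure: 200 × (1 − 0.26) = 148 requiring treatment. It reproduces exactly.
- Complement: 200 − 148 = 52 former active-arm subjects entering clear, 52/400 = 13% of enrolment.
- Subject-time to Day 182 if none is treated later: 52 × 182/365.25 = 25.9 subject-years.

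The 26% is a rate per wart that the protocol applies per subject. Entering clear requires all of a subject's warts to be clear, so the subject-level rate may be lower or higher. Assumed range, not from the documents:

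- 10%: 20 subjects, 20 × 182/365.25 = 10.0 subject-years.
- 40%: 80 subjects, 80 × 182/365.25 = 39.9 subject-years.

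Clear former vehicle subjects are additional, and the documents give no rate for them. If that rate were 0% to 26% (assumption), 52 to 104 of 400 subjects (13% to 26%) would enter clear. If half of all those entering clear later started treatment (assumption), 26 to 52 would remain never treated.

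**The case against.** The strongest reply is that 13.1.3 sets when reporting must start and does not forbid earlier entries. The medical-history sentence covers an interval ending at the first application, which a never-treated subject does not have. A site could reasonably follow Table 3 and 9.3, which were written for these subjects. That is a possible reading, but it depends on each site choosing it, and 12.2 and the last line of 13.1.1 point the other way.

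A second reply concerns importance. Section 4.2 motivates the study by the need for repeated courses, the primary objective concerns twice-weekly application, and the sample size targets repeat-treated subjects. The parent studies already provide "8 weeks of treatment and 12 weeks of post treatment follow up", so on schedule the events at issue begin after that follow-up. This stands, and it limits the weight of the point.

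A reader might also infer several stronger things that the documents do not support:

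- *That the events go unrecorded.* 13.1.3 sends post-consent events before the first application to medical history; what is lost is their status as AEs.
- *That the planned safety tables are distorted.* SAP 3.11 summarises treated subjects only, and SAP 3.11.2 tabulates only AEs within 30 days of an application.
- *That the 'prior' class in SAP 3.11.2 contradicts 13.1.3.* SAEs are reported from consent, so that class can properly contain records.
- *That 13.1.1 contradicts itself by counting laboratory abnormalities after screening.* That text says what an AE may include. A reporting window narrower than the definition is not in itself a contradiction.
- *That the calls escape the open AE question.* 13.2.1 applies to every visit after enrolment, and Table 3 numbers the calls as visits.
- *That the SAP drops the untreated groups of 14.4 silently.* SAP 3.14 states and explains the change, and SAP 3.2 sorts listings by group, including both untreated groups.

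**Conclusion.** The point holds within limits. As written, 13.1.3, 12.2 and the last line of 13.1.1 conflict with Table 3, 9.3, 13.2.1 and the untreated groups of 14.4. The conflict affects non-serious events and clinically significant laboratory results in two situations: throughout the study for subjects never treated in it, and before the first application for subjects treated later. It does not affect SAEs, AEs after A-101 is started in this study, or any SAP summary table. The damage is to AE capture and to the interpretation of the untreated-subject listings.

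The estimate of about 52 former active-arm subjects is an indication of scale, not a bound. It rests on using a per-wart rate per subject, and the 25.9 subject-years also assume that none is treated later. The contradiction itself depends on neither figure. It is worth correcting because a literal reading yields poorer safety data in a study whose primary objective is safety.

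**What to change.** Amend Protocol 13.1.3 so that recording of non-serious AEs starts at WART-303 consent (Visit 1), at minimum for subjects not treated at Visit 1, in line with Table 3. Change the trigger in 12.2 and in the last line of 13.1.1 to match.

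The cost is a wording change in three sections and a short memo to sites. The AE contacts are already in Table 3, so no visit is added. The downside is somewhat more unrelated AEs to enter and code.

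Three further clarifications are optional and the fix does not need them: a sentence in 9.3 confirming that the open question of 13.2.1 is asked on the calls, a category in SAP 3.11.2 for AEs in subjects with no application in this study, and alignment of Protocol 14.4 with SAP 3.14.

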13.1.4. Severity

The investigator must define the severity of each AE using the following definitions as a guideline. The investigator will consider the range of the possible severity of the event and identify the severity that is the most appropriate according to her/his medical judgment.

Mild – Awareness of signs or symptom, but easily tolerated

Moderate – Discomfort, enough to cause interference with usual activity

Severe – Incapacitating with inability to perform usual activity.

13.1.5. Relationship to Study Medication

The investigator will determine if there is a reasonable causal relationship between the study medication and an AE or not. The investigator will use her/his best medical judgment and consider all relevant factors (e.g., temporal relationship, location of the event, the subject's relevant medical history, concomitant therapies and concurrent conditions) to determine the relationship of the AE to the study medication. The investigator will define the relationship of an AE to the study medication by selecting one of the following categories.

Related – There is a reasonable possibility that there is a causal relationship between the study medication and the AE.

Not Related – There is not a reasonable possibility that there is a causal relationship between the study medication and the AE.

The term “reasonable causal relationship” means there are facts or arguments to suggest a causal relationship (International Conference on Harmonization (ICH) E2A).

13.2. Reporting Procedures

13.2.1. Procedures for Reporting Adverse Events

At each post enrollment visit, the investigator or designee will question the subject to elicit AEs using a non-directive question such as “Has there been any change in your health since the previous study visit?”

The Investigator/designee will monitor the subject for at least 20 minutes after the Treatment Completion Time at any visit during which a study medication treatment is performed to elicit AEs in a similar manner.

If appropriate, based on the subject's response to non-directed questioning regarding AEs, the investigator or designee will follow-up with directed questions and appropriate evaluations.

Any AE noted during the reporting period must be reported in the source documents and on the appropriate AE CRF.

AEs that are defined as “Not Related” to the study medications will be followed until they are resolved or until the subject's last study visit. AEs that are defined as “Related” to the study medications will be followed until they are resolved or, if not resolved after the subject's last study visit, until in the opinion of the investigator, the AE reaches a clinically stable outcome with or without sequelae.

13.2.2. Procedure for Reporting Serious Adverse Events

Upon becoming aware of a SAE occurring during the AE reporting period, whether or not related to the study medications, the investigator must:

1. Take the appropriate medical action to ensure the subject's safety
2. Immediately inform the Aclaris of the SAE by entering the event in to the Axiom database. If the Axiom database is unavailable, the site must fax a provided paper SAE form to Aclaris at the number below:

Serious Adverse Event [contact]

3. Within 24-hours of becoming aware of the event, a SAE report form, an AE CRF and any other relevant information (*e.g.*, concomitant medication CRF, medical history CRF, laboratory test results) must be entered in to the Axiom database.
4. Monitor and document the progress of the SAE until it resolves or, if not resolved after the subject's last study visit, until in the opinion of the investigator the AE reaches a clinically stable outcome with or without sequelae AND the investigator and Drug Safety Monitor agree that the SAE is satisfactorily resolved.
5. Inform the Drug Safety Monitor of SAE updates by telephone followed by an SAE form update entered in to the Axiom database.

Comply with the appropriate regulatory requirements and Aclaris Therapeutics, Inc. instructions regarding reporting of the SAE to the responsible Institutional Review Board (IRB) or Ethics Committee (EC).

13.2.3. Withdrawal Due to an Adverse Event

Any patient who experiences an adverse event may be withdrawn from study drug at any time at the discretion of the investigator. If a patient is withdrawn wholly or in part because of an adverse event, both the adverse events page and termination page of the CRF will be completed at that time. The patient will be monitored until the event has resolved or stabilized, until a determination of a cause unrelated to the study drug or study procedure is made, or until the patient is referred to the care of a local health care professional. The investigator must inform the medical monitor as soon as possible of all patients who are being considered for withdrawal due to adverse events. Additional reports must be provided when requested.

14. STATISTICAL CONSIDERATIONS

Details of all statistical summaries and analyses will be provided in the study specific Statistical Analysis Plan (SAP).

14.1. Sample Size and Power Considerations

The sample size is based on an estimate of how many patients will be required to provide at least 100 subjects requiring repeated treatment for a wart over the course of the study.

- By recruiting 400 subjects, we estimate 200 subjects will have received active treatment in the A101-WART 301/302 studies.
- We expected approximately 26% of warts treated in A-101-WART-301/302 studies to be clear at the end of the A101-WART 301/302 studies.
- Based on the assumption that 26% of warts will be clear, at least 148 subjects will require exposure to active treatment.
- We anticipate that some subjects originally randomized to vehicle will be exposed to active treatment.

As a result, the study should exceed the target of exposing more than 100 subjects to repeated treatments over the course of the study.

